# Table 8 - Planned Phase II Statistical Analysis – Treatment/Crossover Group

Predictor Variable	Outcome Variable(s)	Statistic	Expected Outcome
Treatment / Crossover Group	Progression to other invasive OA treatment	Chi-Square	Trend APS Superior

Treatment / Crossover Group	OMERACT-ORSI Responder / Non- Responder	Chi-Square	Trend APS Superior
Treatment / Crossover Group	WOMAC Pain, 6 Mo Intervals	One-Way Anova	Trend APS Superior
Treatment / Crossover Group	WOMAC Function, 6 Mo Intervals	One-Way Anova	Trend APS Superior
Treatment / Crossover Group	NRS Pain, 6 Mo Intervals	One-Way Anova	Trend APS Superior
Treatment / Crossover Group	EQ-5D Global Assessment 6 Mo Intervals	One-Way Anova	Trend APS Superior
Treatment / Cross Over Group	Patient Preference	Chi-Square	Trend APS Superior
Treatment / Cross Over Group	WOMAC Pain Δ: Baseline-12M	Summary Statistics and ANCOVA Model*	Trend APS Superior
Treatment / Cross Over Group	WOMAC Pain ∆: Baseline-6M	Summary Statistics and ANCOVA Model*	Trend APS Superior
Treatment / Cross Over Group	Percent of Subjects in each Treatment/Cross Over Category	Chi-Square	Trend APS Superior

\*Analysis of Covariance models will be used in order to determine if changes in WOMAC Pain score from Baseline to12 months (first model) or from 6 to 12 months (second model) differ according to what type of 2nd injection they chose to receive ( $\beta_3$ ), and whether this difference varies for APS and HA ( $\beta_2$  \*  $\beta_3$ ). The model will be as follows:

 $Y=\beta_0+\beta_1+\beta_2+\beta_3+\beta_2*\beta_3$ 

Where

 $\beta_0$ = Intercept

 $\beta_1$ = Baseline WOMAC Pain score

 $\beta_2$  = Treatment Group

 $\beta_3$ = 2nd Injection (None, Same, Crossover)

Y= Change in WOMAC Pain

In addition to these tests, results of the patient preference questionnaire will be tabulated by crossover group.

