An X-ray will be obtained at 12 months and annually thereafter to assess anatomical changes. Only radiograph images taken up to 24 months of follow-up will be transferred to the Core Imaging Laboratory for independent review. Image acquisition, transfer, and analysis procedures will be performed using validated, prospectively defined methods. All AEs that occur during the 12 month blinded study period will be recorded. In the long-term follow-up phase (12 - 60 months), only events of interest will be recorded.

After each subject completes all 12-month follow-up evaluations, only subjects will be blinded to the individual treatment allocation resulting in single-blind design following 12-month follow-up time point. Subjects from both groups will be able to request additional injections of their originally assigned treatment as frequently⁴ as needed, provided they did not experience any significant clinical concerns after previous treatment administrations and are benefiting from it, as determined by the investigator. During the long-term follow-up phase (12 - 60 months), subjects may also elect to cross over to the other treatment arm and receive additional injections of the other treatment as frequently as needed, provided they did not experience any significant clinical concerns after previous treatment administrations and are benefiting from it, as determined by the investigator. Subjects may only cross over from their originally assigned treatment group to the other treatment group one time during the study. Subjects seeking alternative invasive OA treatment in the index knee who do not wish to cross over or who have already crossed over will exit the study, and their selected treatment option will be recorded.

⁴ Please refer to Synvisc One IFU for specified clinical use requirements.

Study Duration:	Maximum study duration per subject is 62 months: 60 r	nonths from
	treatment to last follow-up, and two additional mo	onths if the
	maximum visit window time is realized.	
Inclusion Criteria:	1. Male or female at least 18 years of age at time of	f screening.
	2. Willingness and ability to comply with study proc	cedures and
	visit schedules and able to follow oral a	and written
	instructions.	
	3. A standing knee radiograph showing a K-L gra	de of 2 to 4
	and an absence of severe osteoarthritis	defined as
	advanced stage osteoarthritis, including large o	steophytes,
	chronic fractures or bone remodeling, severe	deformity or

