# 1.2 Study Design

The study is a two-phase, randomized, double-blind study with a planned enrollment of 246 subjects assigned to treatment groups on a 1:1 basis. It is designed to determine whether APS provides a more effective treatment for knee osteoarthritis than HA. The study will be conducted in two phases. Phase I is the randomized, double-blind portion of the study. After each subject completes all 12 month follow-up evaluations, only subjects will be blinded to the individual treatment allocation resulting in single-blind design following 12-month follow-up time point. Subjects from both groups will be able to request additional injections of their originally assigned treatment as frequently as needed, provided they did not experience any significant clinical concerns after previous treatment administrations and are benefiting from it, as determined by the investigator. During the long-term follow-up phase (12 -60 months), subjects may also elect to cross over to the other treatment arm and receive additional injections of the other treatment as frequently as needed, provided they did not experience any significant clinical concerns after previous treatment administrations and are benefiting from it, as determined by the investigator. Subjects may only cross over from their originally assigned treatment group to the other treatment group one time during the study.

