#### Treatment Success from Original Treatment Assignment

- (1) No cross-over or study exit for other invasive treatment
- (2) Clinically meaningful improvement in WOMAC Pain score (>20% from baseline)

The items in **Table 7** will be analyzed according to the original treatment assignment (APS or HA). The items in **Table 8** will use Treatment / Crossover group as the predictor variable: (1) randomized to APS and not crossed over to HA, (2) randomized to APS and crossed over to HA, (3) randomized to HA and crossed over to APS and (4) randomized to HA and not crossed over to APS. For all tests where the Treatment / Crossover Group is the predictor variable, patients progressing to other invasive treatment for their OA will be included as a Non-Responder (where OMERACT-OARSI responder is the outcome variable) or using the most recently collected outcome score (where pain, function or EQ-5D is the outcome variable).

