# Table 7. Planned Phase II Statistical Analysis-Originally AssignedTreatment

Predictor Variable	Outcome Variable(s)	Statistic	Expected Outcome
Treatment Group	Election to Cross Over	Fisher's Exact	Statistically Significant, More HA than APS Cross Over
Treatment Group	Percentage of patients achieving	Fisher's Exact	APS Superior

	treatment success from initial injection		
Treatment Group	Percentage of patients achieving treatment success from originally assigned treatment	Fisher's Exact	APS Superior
Treatment Group	Percentage of patients achieving success in each treatment arm (i.e. patients with clinically meaningful improvement in WOMAC Pain score, inclusive of originally assigned and cross-over patients)	Fisher's Exact	APS Superior
Treatment Group	Average number of cumulative interventions per patient	Likelihood Ratio Chi-Square	Trend APS Superior
Treatment Group	Time from the initial injection (nSTRIDE APS or HA) to first subsequent injection, cross- over, or study exit for other invasive treatment	Kaplan Meier – Time to first subsequent injection/cross- over/other invasive treatment	Trend APS Superior

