# 7. Data Collection Time Points

Data will be collected at the screening visit, the injection visit, and at 1, 3, 6 and 12 months following the injection. After each subject completes all 12 month follow-up evaluations (Phase I), individual treatment allocation will be unblinded to the investigators. From this time-point on, only subjects will be blinded to study treatments resulting in a single-blind design during the longterm follow-up period (Phase II). During Phase II of the study, the subject may opt to get additional injections of their originally assigned treatment, or they may opt to crossover to the other treatment group and may receive multiple injections of the crossover treatment. Subjects may only crossover one time during the study. In Phase II, follow-up visits will occur at six month intervals until five years following the initial injection.

The follow-up visits will preferably be completed during an office visit to ensure subject compliance, but this is not mandatory and follow-up visits may consist of a structured telephone interview or electronic self-report with exception of annual visits at which radiograph is to be taken. The investigative center will contact the subject to complete the Follow-up and AE forms. The subject will be asked to complete a Patient Questionnaire.

A table showing the data collected at each time interval is presented in the study protocol.

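### Table 8, row 1 compares progression between groups defined by ever crossing over, so the test contains immortal-time bias, and its p-value measures neither product's effect nor the effect of crossing

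*SAP*

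**What the plan says.** SAP section 4.5 states that the Table 8 items "will use Treatment / Crossover group as the predictor variable". Two groups come from the APS arm, crossed and not crossed. The other two are "3) randomized to HA and crossed over to APS and (4) randomized to HA and not crossed over to APS". The first row of Table 8 takes "Progression to other invasive OA treatment" as outcome, a chi-square as test, and a trend in favour of APS as expected result. It gives no time origin, censoring rule, landmark or person-time denominator.

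SAP section 1.2 says that in months 12 to 60 "subjects may also elect to cross over to the other treatment arm", once only. The protocol synopsis (Study Design and Procedures) adds: "Subjects seeking alternative invasive OA treatment in the index knee who do not wish to cross over or who have already crossed over will exit". SAP section 7 says "follow-up visits will occur at six month intervals until five years following the initial injection".

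Two other provisions come close to the point:
- Section 4.5 has a rule for subjects who progress. It covers responder status and pain, function and EQ-5D scores, not progression itself.
- Table 7 has a Kaplan-Meier analysis by randomised arm. Its event is a composite in which a further injection or a cross-over also counts.

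SAP section 1 makes all Phase II analyses exploratory, at an unadjusted 0.05.

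**The concern.** Group membership in this row is settled by what happens during follow-up, and the outcome can prevent membership. Once a subject leaves for other invasive treatment, crossing is no longer possible, so that subject is always an event in a not-crossed group. A crosser must have remained free of progression up to the crossing date, and that event-free time is credited to the crossed group. This is immortal-time bias. It needs no link between crossing and prognosis and is distinct from self-selection.

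Row 1 is also the only planned test of progression as an outcome in its own right. A small p-value could be reported as evidence about the products, or about crossing, when neither has any effect.

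**Working it through.** The plan states no rate or power for this row, so there is no figure to reproduce. The size was examined under assumed rates.

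**Inputs from the documents:** 246 subjects randomised 1:1, so 123 per arm; cross-over open from month 12 to month 60, so T = 4 years; exit at progression; four groups as in section 4.5; test level 0.05.

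**Assumptions:** constant progression hazard l and crossing hazard c from month 12; l unchanged by arm or by crossing (no true effect); no other drop-out; progression counted in Phase II only.

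**Closed form with independent hazards.** Let E = 1 − exp(−(l + c)T).
- P(crossed) = c/(l + c) × E
- P(progressed before crossing) = l/(l + c) × E
- P(progressed by T) = 1 − exp(−lT)
- Progression in not crossed = P(progressed before crossing) / (1 − P(crossed))
- Progression in crossed = (P(progressed by T) − P(progressed before crossing)) / P(crossed)

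APS arm, l = 0.10, c = 0.10: E = 1 − exp(−0.8) = 0.551, so P(crossed) = P(progressed before crossing) = 0.275; P(progressed by T) = 1 − exp(−0.4) = 0.330. Not crossed: 0.275/0.725 = 38%. Crossed: (0.330 − 0.275)/0.275 = 20%.

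HA arm, l = 0.10, c = 0.20: E = 1 − exp(−1.2) = 0.699; P(crossed) = 0.466; P(progressed before crossing) = 0.233. Not crossed: 0.233/0.534 = 44%. Crossed: (0.330 − 0.233)/0.466 = 21%.

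Every subject has the same 33% risk over four years. The classification alone produces the gaps.

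**Simulated rejection by the four-group Pearson chi-square, no true effect, 123 per arm:**

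| Progression per year | Crossing per year, APS / HA | Rejection |
|---|---|---|
| 10% | 10% / 20% | about 81% |
| 5% | 10% / 20% | about 56% |
| 5% | 5% / 5% | about 12% |
| 2% | 5% / 10% | about 7% |

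The row does not say whether Phase I exits count. If they do, the gap widens: at l = 0.05 and c = 0.20, crossed is 10.8%, against 25.6% in not crossed for Phase II alone and 32.6% with Phase I.

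**Crossing linked to prognosis.** The first setting was repeated with one log-normal frailty multiplying both hazards, so that worse knees cross more and progress more. There is still no true effect.

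| Frailty SD | Chi-square rejection | Direction | Progression rate ratio, after vs before crossing, unadjusted |
|---|---|---|---|
| 0.5 | about 43% | crossers lower | about 1.2 |
| 1.0 | about 5% | none (APS 27% not crossed, 28% crossed; HA 28% and 27%) | about 2.0 |
| 1.5 | about 33% | reversed (APS 20% and 31%; HA 19% and 30%) | about 3.3 |

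The last column is what a time-dependent cross-over analysis shows without adjustment. Under independent hazards the ratio is about 1, so allowing for time removes the immortal-time part. It leaves the selection part in full.

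**The case against.** The strongest reply is that independence between crossing and progression fits this protocol poorly. The synopsis presents cross-over and exit for invasive treatment as alternative responses to the same need, so worse knees plausibly raise both. Selection then offsets the immortal time, and at a frailty SD of 1.0 the planned test happens to sit at its nominal level. This stands, and it limits what can be claimed.

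A reader might infer that crossing will always look protective. The documents do not support that, because the direction depends on an unknown association.

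A reader might also infer that the artefact will be taken as APS superiority, since the SAP expects "Statistically Significant, More HA than APS Cross Over" and a trend favouring APS in this row. That does not follow either. A four-group chi-square has no direction, and in the first setting the artefact favours APS-to-HA crossers (20%) as much as HA-to-APS crossers (21%).

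Two further replies have weight. The largest rejection rates need high assumed hazards: 10% a year is 33% over four years with no other drop-out. And the row is exploratory, with no success criterion attached.

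None of this repairs the row. A test that is near nominal only when two biases happen to cancel is not a valid test. The section 4.5 rule and the Table 7 composite do not separate the time before crossing from the time after it.

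**Conclusion.** The defect holds as a matter of structure: groups fixed by ever crossing, an outcome that rules out later crossing, and a test that ignores time. Immortal-time bias is therefore present and, taken alone, lowers apparent progression in crossers.

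Its size rests wholly on assumed rates: about 7% to 81% rejection against a nominal 5% under independence, and about 43%, 5% and 33% with increasing shared frailty, reversed in direction at the last. Net direction and size in the real data cannot be predicted. What can be said is that the p-value measures neither the effect of either product nor the effect of crossing.

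The change is worth making. The consequence is confined to one exploratory Phase II row and does not touch the primary test.

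**What to change.** In Table 8, row 1:

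1. Report the four-group percentages as description only, and delete the chi-square and the expected trend.
2. Make the inferential analysis of progression a time-to-event comparison by randomised arm, from the initial injection and without censoring at cross-over.
3. If an analysis by cross-over is kept, enter cross-over as a time-dependent covariate that switches at the first cross-over injection. Include an arm-by-cross-over interaction, so that APS-to-HA and HA-to-APS do not share one coefficient. Adjust for the most recent WOMAC pain and function before crossing, and label the result non-causal. A model with arm and cross-over status alone should not be used, given the false rate ratios of about 1.2 to 3.3 shown above.

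Cost: SAP wording and one or two models. Injection and exit dates are already needed for the Table 7 Kaplan-Meier analysis, and the protocol already records the treatment chosen at exit. The by-arm comparison is diluted by crossing, and intervals for the period after cross-over will be wide.

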Secondary objectives of this study include determining whether nSTRIDE APS is superior to HA in improving WOMAC LK 3.1 function at 12 months (as evaluated using the percentage of subjects showing at least the minimal clinically important difference (MCID)), and WOMAC LK 3.1 pain at 12 months (as evaluated using the percentage of subjects showing at least the minimal clinically important difference (MCID)), OMERACT-OARSI responder rates at 12 months, analyzing WOMAC pain and function in only the KL-II Subgroup at 12 months, evaluating superiority of APS over HA in improving Numeric Rating Scale (NRS) pain at 12 months, assessment of the changes in WOMAC Pain scores over time (baseline through 12 months), and evaluation of the usage of rescue medication within 12 months. These will be tested in a fixed sequential order pending the rejection of the primary null hypothesis.

Exploratory objectives of this study include determining whether APS is superior to HA with regards to improvement in mean EQ-5D outcomes (12 months minus baseline) and repeated measures of WOMAC Function, WOMAC stiffness, and total WOMAC score. In addition, changes in joint morphology (determined with X-ray images) will be evaluated. Subgroup analyses will be conducted to investigate whether the treatment effect varies depending on subjects' initial pain and baseline information. Analysis of exploratory endpoints will be done using alpha=0.05 with no adjustment for multiple comparisons.

A long-term follow-up phase will examine the superiority of nSTRIDE APS in the duration of the treatment effect, injection frequency, patient preferences, healthcare resource utilization, and associated costs. These endpoints will be treated as exploratory endpoints and analyses will be conducted using alpha = 0.05 with no adjustment for multiple comparisons.

Finally, the safety profile of nSTRIDE APS will be compared to HA by comparing adverse events and rates between treatment groups.

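### As written, the last row of SAP Table 8 tests treatment/crossover group against itself, so its chi-square says nothing about APS versus HA

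*SAP*

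**What the plan says.** Section 4.5 of the SAP separates two sets of Phase II analyses. Table 7 is analysed by randomised arm. The items in Table 8 "will use Treatment / Crossover group as the predictor variable: (1) randomized to APS and not crossed over to HA"; level 2 is APS crossed to HA, and the list ends with "randomized to HA and crossed over to APS and (4) randomized to HA and not crossed over to APS". The predictor therefore has four levels, which combine the randomised arm with whether the subject crossed over.

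The last row of Table 8 has this group as predictor, "Percent of Subjects in each Treatment/Cross Over Category" as outcome, chi-square as statistic and "Trend APS Superior" as expected outcome. The SAP gives no null proportions, no separate definition of the category and no other predictor for the row. The footnoted ANCOVA model is attached to the two WOMAC pain rows above it, not to this one.

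The first row of Table 7 already tests "Election to Cross Over" by randomised arm with Fisher's exact test. Section 1 says of the long-term endpoints that "analyses will be conducted using alpha = 0.05 with no adjustment for multiple comparisons".

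**The concern.** A chi-square test of association needs two different variables. Here the only outcome the row names is the classification that already serves as predictor, so a programmer following Section 4.5 would cross-tabulate the group with itself. The resulting p-value would be extremely small however the two products performed, and it would be reported under an expected outcome that favours APS. The SAP does not say which other test might be meant.

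The stake is limited but real. Section 1 lists injection frequency and patient preference among the long-term questions. How each randomised arm divides between no further injection, more of the same product and crossing over bears on both, and this row looks like the place where that was meant to be examined.

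**Working it through.** The SAP states no figure for this row, so there is none to reproduce. The check is what the row would return under each reading.

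**Inputs**
- N: Section 1.2 gives a "planned enrollment of 246 subjects assigned to treatment groups on a 1:1 basis", so 123 per arm. Section 6.1 also gives 93 per arm (N = 186) before the attrition allowance.
- Predictor: four levels, from Section 4.5.
- Crossover rates: not in the documents. All rates below are assumptions, shown over a range.

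**Reading 1: group against itself (literal)**

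With k non-empty groups the table is diagonal, and Pearson chi-square = N(k−1) on (k−1)² df.
- N = 246, k = 4: 246 × 3 = 738 on 9 df, p ≈ 5 × 10⁻¹⁵³.
- N = 186, k = 4: 186 × 3 = 558 on 9 df, p ≈ 2 × 10⁻¹¹⁴.
- N = 246, nobody crosses over, k = 2: 246 × 1 = 246 on 1 df, p ≈ 2 × 10⁻⁵⁵.

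The 5% critical values are 3.84 (1 df), 9.49 (4 df) and 16.92 (9 df). N(k−1) exceeds them once N reaches 4, 5 and 6 for k = 2, 3 and 4. At N = 246 with four groups, the value 738 was the same for 20% crossover in both arms, 10% in APS v 40% in HA, 40% v 10%, and 50% in both.

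**Reading 2: one-sample test that the four groups are equal in size**

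The expected count is 246/4 = 61.5 per group. If the same proportion p crosses over in each arm, the observed counts are 123(1−p), 123p, 123p and 123(1−p), and chi-square = 246(1−2p)² on 3 df.

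| Assumed crossover, both arms | Chi-square |
|---|---|
| 0% | 246.0 |
| 10% | 246 × 0.64 = 157.4 |
| 20% | 246 × 0.36 = 88.6 |
| 30% | 246 × 0.16 = 39.4 |
| 40% | 246 × 0.04 = 9.8 |
| 50% | 0 |

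The arms are identical in every line of this table. Only the distance of the crossover rate from 50% moves the statistic. With whole-number counts:
- 20% in both arms (98, 25, 25, 98): 4 × 36.5²/61.5 = 86.7.
- 10% in APS v 40% in HA (111, 12, 49, 74): (2 × 49.5² + 2 × 12.5²)/61.5 = 84.8. Reversing the arms gives the same 84.8.

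So two identical arms can give a larger statistic than two very different ones, and the direction of a difference leaves no trace.

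**Reading 3: four-level group by second injection (none, same, crossover)**

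The crossover cells are still fixed by the predictor. In 4,000 simulated trials with 123 per arm, 20% crossover in both arms and 30% of the remainder repeating the same product (all assumed), the test rejected every time.

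**For comparison: randomised arm by crossed over, yes or no**

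This test responds to the data. With 25/123 in each arm, Fisher's p = 1.0. With 12/123 in APS v 49/123 in HA, p ≈ 5 × 10⁻⁸. In the same simulated trials with equal 20% crossover it rejected in 3.5%. It is also the first row of Table 7.

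**The case against.** The strongest reply is that the self-association may not be what the authors meant. The two rows directly above carry nearly the same predictor label, yet their footnote splits it into treatment group, second injection (none, same, crossover) and the interaction. Read that way, the last row would be arm by type of further injection, which is informative. This stands as a guess at intent. It does not cure the text, because the footnote is not attached to this row and Section 4.5 fixes the four-level predictor for the whole table.

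Three stronger inferences are tempting, and the documents do not support them.
- *That the row guarantees a false claim of APS superiority.* The superiority wording is an entry in the expected-outcome column, used throughout Table 8. It is not a conclusion triggered by p < 0.05, no success criterion depends on it, and a diagonal table would probably be noticed when produced.
- *That the result is significant whatever the data.* This holds for the literal reading only. The equal-sizes test returns 0 at 50% crossover in both arms. The value 738 also needs N = 246 and four non-empty groups, and 246 is planned enrolment before attrition.
- *That further treatment is not compared by arm anywhere.* Table 7 also compares the cumulative number of interventions, time to the first further injection, crossover or exit for other invasive treatment, and success from the initial injection, which requires no additional injection. Only the three-way split is missing.

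**Conclusion.** The row is wrong as written. On the literal reading the statistic is N(k−1), fixed by the sample size and the number of occupied groups and significant at any realistic N. On the equal-sizes reading it measures how far crossover lies from 50%. Neither compares APS with HA. The first result is algebra and needs no assumption about outcomes; the figures for the second rest on assumed crossover rates.

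The consequence is small. The analysis is exploratory and unadjusted, lies outside the fixed testing sequence, and touches no primary or secondary conclusion. What would be lost is one interpretable Phase II comparison, and what would be gained is a p-value without meaning. It is worth correcting because the correction is so cheap.

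**What to change.** Either of two changes is enough.

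1. Replace the row with randomised arm (APS, HA) by further treatment over Phase II, in three categories: none, same product only, ever crossed over. Use a chi-square or exact test, and move the row to Table 7, where the predictor is already the original assignment. Define the categories over the whole of Phase II. The footnote's second-injection factor should not be reused unchanged, because a subject who repeats the original product and crosses over later would be counted as having had the same product. State the denominator: a table restricted to subjects entering Phase II conditions on retention to 12 months and is no longer the full randomised comparison.

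2. Report the four group sizes as n and % with no p-value and no expected outcome, and rely on the "Election to Cross Over" test in Table 7.

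The cost is one table row and, for the first option, a sentence of definition. The data are already to be collected.

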	nSTRIDE APS is superior to HA with regard to the improvement in
	mean Western Ontario and McMaster Universities Osteoarthritis
	Index (WOMAC) LK 3.1 pain score (change from baseline to 12
	months post-injection).
	Secondary Objectives
	Secondary objectives of this study include determining whether
	nSTRIDE APS is superior to HA in improving WOMAC LK 3.1
	function at 12 months (as evaluated using the percentage of
	subjects showing at least the minimal clinically important difference
	(MCID)), and WOMAC LK 3.1 pain at 12 months (as evaluated
	using the percentage of subjects showing at least the minimal
	clinically important difference (MCID)), OMERACT-OARSI
	responder rates at 12 months, analyzing WOMAC pain and
	function in only the KL-II Subgroup at 12 months, evaluating
	superiority of APS over HA in improving Numeric Rating Scale
	(NRS) pain at 12 months, assessment of the changes in WOMAC
	Pain scores over time (baseline through 12 months), and
	evaluation of the usage of rescue medication within 12 months.
	Exploratory Objectives

	Exploratory objectives of this study include determining whether nSTRIDE APS is superior to HA in improving patient reported outcomes including pain, function, stiffness, and quality of life in subjects with early to moderate symptomatic OA. A long-term follow-up phase will examine the superiority of nSTRIDE APS in the duration of the treatment effect, injection frequency, patient preferences, healthcare resource utilization, and associated costs.
	Safety Objectives Safety of nSTRIDE APS will be compared to HA following intra- articular knee injections in subjects with early to moderate symptomatic OA.
Study Design and Procedures:	The study will compare the efficacy of nSTRIDE APS injection to HA in patients with symptomatic OA in one knee, who have failed at least one prior conservative OA therapy (e.g. physiotherapy, simple analgesics). This will be done using a double-blind, multicenter, Randomized Controlled Trial (RCT) with study subjects receiving either a single injection of nSTRIDE APS or HA. The primary efficacy measure will be pain as measured utilizing the WOMAC LK 3.1 scale; other measures of efficacy will include function, stiffness, and quality of life. In addition to clinical efficacy measures, safety will be assessed by tracking adverse events (AEs).

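### The Table 8 ANCOVA relates pain change complete by month 12 to a second injection chosen only afterwards, so it can describe later choosers but cannot show an effect of that injection; its second model also has two conflicting intervals

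*SAP*

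**What the plan says.** The last part of SAP Table 8 (Section 4.5) has two rows analysed by ANCOVA, one for WOMAC Pain change from baseline to 12 months and one for baseline to 6 months. Both rows expect a trend favouring APS. The footnote describes the outcomes as changes from "Baseline to12 months (first model) or from 6 to 12 months (second model) differ according to what type of" second injection the subject chose. The model contains baseline WOMAC Pain, treatment group, the second "Injection (None, Same, Crossover"), and the interaction of the last two. The response is defined only as "Y= Change in WOMAC Pain", with no interval.

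The timing of injections is stated elsewhere. The Protocol synopsis (Study Design and Procedures) has subjects "receiving either a single injection of nSTRIDE APS or HA". SAP Section 7 says: "During Phase II of the study, the subject may opt to get additional injections of their originally assigned treatment". SAP Section 1.2 says that in the long-term phase, months 12 to 60, "subjects may also elect to cross over to the other treatment arm and receive additional injections of the other treatment as frequently as needed". The same section makes further injections conditional on subjects having no significant clinical concerns and on whether they "are benefiting from it, as determined by the investigator". For election to cross over, Table 7 expects: "Statistically Significant, More HA than APS Cross Over".

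SAP Section 1 classes the long-term endpoints as exploratory, tested at 0.05 without adjustment.

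**The concern.** The outcome comes before the predictor. A subject's pain change up to month 12 is fixed before that subject can choose a repeat or crossover injection. An association between the two can show that subjects with a poorer or better first year chose differently. It cannot show what the second injection did. A significant term, set beside an expected trend favouring APS, could easily be reported as a benefit or harm of re-injection or crossover.

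The same model also yields an APS-HA coefficient adjusted for a choice that probably depends on the outcome. That coefficient no longer estimates the randomised contrast.

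Separately, the second model has two definitions. Two analysts following the SAP could analyse different outcomes under the same table row.

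**Working it through.** The SAP attaches no figure to this ANCOVA, so there is none to reproduce. The timing and the intervals are checked from the text. A simulation then illustrates the consequence.

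**1. Timing**

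| Item | When it is fixed | Source |
|---|---|---|
| Change, baseline to 12 months | Month 12 | Table 8 row and footnote |
| Change, baseline to 6 months | Month 6 | Table 8 row |
| Change, 6 to 12 months | Month 12 | Table 8 footnote |
| Repeat of same treatment | After the 12-month evaluations | SAP 1.2 and 7 |
| Crossover | Months 12 to 60 | SAP 1.2 |

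Every candidate outcome ends at or before month 12, and every second injection comes later. Counting the months from the second injection does not rescue the model. Neither the rows nor the footnote says so, the None group has no such date, and the covariate is the study baseline score. Where the SAP does restart the clock, in Tables 13 and 14, the first column is headed with the second injection.

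**2. Interval**

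Change (0 to 12) = change (0 to 6) + change (6 to 12). The row takes the first part and the footnote the second, so the two definitions do not overlap. If the footnote governs, the starting value is the 6-month score, but the model adjusts for baseline.

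**3. Illustration of selection**

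Inputs from SAP Table 15 and Section 6.1: mean improvement 4.93 (saline, which the SAP assumes HA resembles) and 7.20 (APS), difference 7.20 − 4.93 = 2.27, SD 4.06, 93 per arm. Assumptions not in the documents:

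- Baseline pain is normal with mean 12 and SD 2.5, rounded and limited to 9 to 19, and unrelated to improvement.
- The choice is drawn after the outcome, so its true effect on the outcome is zero.
- With z = (improvement − 6.07)/4.06, the log-odds against None are −0.7 − 0.3gz for Same and −0.7 − gz for Crossover.
- An optional offset adds 1 to the HA log-odds of Crossover.

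There were 2,000 runs per setting. The second-injection results come from the model without interaction, with a true arm difference of 2.27 and no offset. The APS-HA results come from the full footnote model, averaged equally over the three choices. Percentages are rejection rates at 0.05.

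| g | Crossover vs None (true 0) | Second-injection term significant | APS-HA, true 2.27, no offset | APS-HA, true 2.27, HA offset | APS-HA, true 0, HA offset |
|---|---|---|---|---|---|
| 0 | 0.0 | 5.5% | 2.26 (94%) | 2.25 (92%) | 0.02 (4%) |
| 0.5 | −2.0 | 67% | 2.19 (94%) | 1.79 (79%) | −0.38 (8%) |
| 1 | −3.5 | 99.6% | 1.98 (91%) | 1.34 (57%) | −0.61 (17%) |
| 2 | −5.3 | 100% | 1.50 (80%) | 0.78 (26%) | −0.75 (26%) |

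With a true difference of 0 and no offset, the APS-HA term is unbiased (−0.01 to 0.01) at every g.

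Leaving out the second-injection terms (change on baseline and arm, no offset) gives 2.24 to 2.28 for a true 2.27, and −0.02 to 0.01 for a true 0 with 4.6% to 4.8% rejection.

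**The case against.** The strongest reply is that the footnote claims no effect. It asks whether changes differ by the injection chosen, and the SAP revision history describes the model as a way to analyse trends across treatment/crossover groups. Comparing earlier response between later choosers is a coherent descriptive question. The terms the footnote names are the second injection and its interaction with arm, not the APS-HA term. The 12-month comparison is the primary t-test, which this model does not touch. All of this stands. It does not explain the expected trend favouring APS, which answers a different question, and it leaves the interval conflict in place.

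Three stronger readings are tempting but not supported:

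- **A reader might infer that the APS-HA term always shrinks toward zero, by a quotable percentage.** There is no distortion when choice is unrelated to response. With a true difference of 0 and more HA crossover, the estimate moves away from zero. The amounts rest on a choice model that the documents do not supply.
- **A reader might infer that repeat injections mark poor responders.** The benefit condition could select better responders into Same. If poor response drives both choices (log-odds falling by 0.1 to 0.3 per point for Same and twice that for Crossover), Same against None is −1.5 to about −3 points. With a positive slope for Same it is about +0.8 to +1.8. The sign is an assumption.
- **A reader might infer that pain after crossover is not analysed.** Table 8 plans WOMAC Pain at 6-month intervals by treatment/crossover group. What is missing is narrower: no planned analysis states a change from a score taken before the second injection.

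**Conclusion.** The point holds on the text alone in two respects. As written, neither ANCOVA can show an effect of the second injection, because the outcome is complete before the choice. And the second model has two incompatible outcomes. Neither conclusion needs an assumption.

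Distortion of the second-injection and APS-HA terms is conditional on choice depending on 12-month response. The benefit condition and the expected excess of HA crossover make that likely. Its size and direction are unknown. In the illustration the APS-HA estimate ranged from 2.26 to 0.78 for a true 2.27, and from 0.02 to −0.75 for a true 0 with more HA crossover. These figures show what can happen and are not forecasts.

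The consequence is confined to two exploratory rows. They should be corrected before they are run, because a plausible misreading would credit or blame an injection not yet given.

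**What to change.** 1. State one interval for the second model in both row and footnote. If 6 to 12 months is kept, use the 6-month WOMAC Pain score as the covariate.
2. Label both models as describing who chooses which injection, and remove the expected trend favouring APS from both rows. Take the 12-month APS-HA contrast only from a model without the second-injection terms.
3. If pain after a second injection is of interest, add the change from the last scheduled WOMAC Pain score before that injection to the next scheduled visits, adjusted for that score. Report it as non-randomised and subject to regression to the mean, since subjects may seek injections when pain is high. Either leave None subjects out or give them a stated reference visit. Use scheduled scores: the Protocol synopsis lists interim visits but states no WOMAC at them.
4. While editing, align the predictor. Section 4.5 announces four groups for Table 8, whereas this model has 2 × 3 = 6 cells.

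The cost is wording for two rows and a footnote, plus a small exploratory analysis of scheduled scores if item 3 is adopted. The downside is a more limited interpretation of these rows.
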